The purpose of this study is to understand whether the couple therapy that is used in practice is effective in preventing situational couple violence. More specifically, we will focus on couples with mild to moderate forms of situational couple violence to investigate how couple therapy can be effective in preventing the escalation and recurrence of situational couple violence. For this purpose, the response of partners to therapy will be investigated by integrating self-report questionnaires and psycho-physiological markers of emotion. All couples who exhibit characteristics of characterological violence will be excluded from the study.

The change in partners' emotion regulation over the course of therapy will be measured using psycho-physiological markers of stress response. Using these measurements, the interplay between changes in violence and the emotion regulation of partners in relation to each other will be investigated in a dyadic (couple) context. More specifically, the following aims will be pursued to understand the relationship between couple therapy, emotion regulation, and violence:

Aim 1: Examine the associations between IPV and each partner's psychophysiological regulation in terms of Hypothalamic Pituitary Adrenal (HPA) activity and Parasympathetic Nervous System (PNS) activity. This aim will investigate whether dysregulation of HPA and PNS activity in each partner is correlated with the existence and intensity of IPV for the couple. Existence and intensity of IPV will be assessed using self and partner report questionnaires. HPA activity will be measured using salivary cortisol, and PNS activity will be measured using vagal tone and vagal regulation by using an eMotion Heart Rate Variability (HRV) sensor.

Aim 2: Examine the longitudinal effects of conjoint therapy on IPV and each partner's psychophysiological regulation in terms of HPA and PNS activity. This aim will investigate whether the reported intensity of IPV for couples decreases after couples start therapy and whether this change is correlated with regulation of HPA and PNS activity for each partner. This aim will examine the effect of couple therapy on each individual partner separately.

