Aim 3: Examine the longitudinal effects of partners' psychophysiological regulation on each other's psychophysiological regulation and on IPV. This aim will explore patterns of change in each partner's psychophysiological regulation as a function of their partner's psychophysiological regulation. More specifically, this aim will investigate whether couple therapy facilitates change by restructuring the relationship in such a way that the change in one partner's behavior helps the other partner regulate their emotions in a functional way.

Principal Investigator: [name]

Protocol Summary for IRB: Feasibility Study of Couple Therapy Treatment for Situational Couple Violence (IRB# 09-13-27)

Study Design

This study has a longitudinal design that requires therapy sessions over 8 weeks, with data collected at every visit. Couple therapy will be conducted using an attachment and affect regulation based therapy approach described below under “Couple Therapy”. Data will be collected in the form of self-report and partner-report measures, as well as physiological screening of the neuroendocrine system. These measures are described below under “Data Collection”. The flowchart for the design of the study is shown below.

After careful screening, eight couples will be enrolled in the study. The couples will be divided into two groups, each consisting of four couples. Distribution of participants to the two groups will be randomized. Group 1 will immediately begin 8 weeks of couple therapy and Group 2 will complete 8 weeks of couple therapy after an 8 week (+ or – 10 days) waiting period is completed.

The pre-test, post-test, and follow-up physiological data collection will be completed at the following times for couples beginning the 8 weeks of couple therapy:

- Baseline Pre-test: Before starting the therapy sessions.
- Post-test: One week (+ or – 5 days) after the end of the therapy session.
- Follow-up: Three months (+ or – 10 days) after the post-test.

The participants that are assigned to Group 2 will also complete the physiological data collection before starting the 8 week waiting period. When participating in the 8 week couple therapy Group, participants will complete a small number of assessments at each therapy session.

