The participants that are assigned to Group 2 will have one additional assessment session at baseline. In order to help those in Group 2 who will not be receiving therapy for the first 8 weeks, individuals in this group will be taught safety planning, given information on local resources to help victims of violence, and will be instructed in stress and anger management strategies. Following this 8 week waiting period, they will receive 8 weeks of couple therapy unless they choose not to. All the physiological and behavioral data collection will be repeated once Group 2 starts therapy.

If a couple discontinues after the baseline and before the end of the study (EOS), the EOS assessments should be obtained.

For couples in Group 1, involvement in the study will last throughout a period of five months with approximately 14 hours of active participation. For couples in Group 2, involvement in the study will last throughout a period of seven months with approximately 16 hours of active participation.

Couple Therapy

Each couple will receive couples therapy for 8 weekly sessions. Each therapy session will last approximately an hour. The therapy sessions will take place in UH Mood Disorders Program, room #12-126, on the 12th floor of the W.O. Walker Center. An attachment and affect regulation based therapy approach will be used in couple therapy.

Principal Investigator: [name]

Protocol Summary for IRB: Feasibility Study of Couple Therapy Treatment for Situational Couple Violence (IRB# 09-13-27)

The participants will receive standard couples therapy that they would have access to outside of the study. The therapy itself is not experimental, but rather it is the data collection, physical measures, and timing which are the experimental portions of the study.

All therapies will be conducted by the PI, [name]. [name] is a Licensed Marriage and Family Therapist and AAMFT (American Association of Marriage and Family Therapy) approved clinical supervisor.

Hypotheses

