- 5) Both partners must want couples therapy and both partners must desire to maintain the relationship.
- 6) Both individuals from the couple must participate concurrently, although they will sometimes be separated when asked questions of a sensitive nature.
- 7) Only heterosexual couples will be included in the study.
- 8) Both partners can be on psychotropic medication, if they are on medication and stable for past 12 month prior to enrollment, and no psychiatric hospitalization for past 2 years.

Exclusion Criteria:

- 1) Couples will be excluded from the study if there are indicators of severe intimate partner violence and/or characterological violence as this study targets couples with mild to moderate levels of violence. In order to distinguish between these two different types of violence, we will use specific items in the Conflict Tactic Scale (CTS) completed by both parties (Johnson, & Leone, 2005).

Severe and/or characterlogical violence in this study is defined as follows:

- If participants answer yes to both of the following items: "I punched or hit my partner with something that could hurt", "I kicked my partner".
- If participants answer yes to any of the following items: "I choked my partner," "I slammed my partner against a wall," "I beat up my partner" "I burned or scalded my partner on purpose," and "I used a knife or gun on my partner".
- One of the partners reports that a violent behavior was repeated at least six times in a year by their partner or themselves.

If one of the partners indicates that any of these behaviors was exhibited by their partner or by themselves, the couple will be excluded from the study. In other words, these behaviors will not be scored, the scale will be used to detect the existence of any of these behaviors and exclude the couple in the case any of these behaviors exist.

This conceptually based classification has been supported by factor analyses and by a growing recognition that the etiology and treatment of occasional minor violence (situational couple violence) may be quite different than the etiology of repeated severe assaults (characterlogical violence) (Gelles 1991; Hollzworth-Munroe and Stuart 1994; Johnson and Ferraro 2000; Straus and Gelles 1990).

- 2) Participants will also be excluded from the study if they answer yes to the following questions: "Do you have any firearm at home?", "In your previous relationships, did your partners ever tell you that you were physically abusive?"

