Table 2. Assessment schedule

Principal Investigator: [name]

Protocol Summary for IRB: Feasibility Study of Couple Therapy Treatment for Situational Couple Violence (IRB# 09-13-27)

Efficacy & Data Analysis

Data analysis plan

This study is designed to be an initial feasibility study to collect pilot data in pursuit of the following aims:

Aim 1: After the first wave of data collection (pretest), the cross sectional relations among the basic constructs of interest will be examined. These basic constructs are psychophysiological markers of emotion regulation and IPV. In order to understand how these markers are related to violence, t-tests will be used to understand this effect. Each partner's HPA and PNS activity is expected to be directly linked to the violence perpetrated by their partner.

Aim 2: The objective of this aim is to understand whether violence decreases over time following therapy and whether this decrease is accompanied by respective change in physiological markers of emotion regulation. For this purpose, series of chi-square-test will be used as well as qualitative analysis.

Aim 3: In order to represent the interaction between the emotion regulation of partners, links from emotion regulation of each partner to the emotion regulation of the other partner at the next time point are included. Qualitative analysis with a grounded theory approach will be used.

The proposed sample size (8 couples) is chosen as a tradeoff between data collection time and statistical power. Since this is a feasibility study, we chose to start with a small sample size. GPower was used to estimate statistical power for the primary hypotheses. Assuming 8 couples (16 participants), with 4 couples in each group and two waves of data each, the statistical significance can be detected. Specifically, with power = .40, this study can detect an effect size of $f = .80$ (Using t-test statistics). Also chi-square test will be used to test the effectiveness of the intervention with power = .40. With this level of power, this study can detect an effect size of $f = .60$ (Using chi-square statistics).

The PI will continually monitor the study design to determine if there is a need to make modifications or discontinue the study due to lack of efficacy from therapeutic intervention.

Safety

Compensation for research related injury

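### Aim 2 is worded as a before/after question although couples are randomised, and the implied comparison of the two groups is not defined

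*Combined protocol and SAP*

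**What the plan says.** Aim 2 is stated twice. In the Data analysis plan: "The objective of this aim is to understand whether violence decreases over time following therapy". Under Purpose, the aim is to investigate "whether the reported intensity of IPV for couples decreases after couples start therapy", followed by "This aim will examine the effect of couple therapy on each individual partner separately". Neither statement names Group 1 against Group 2. The methods given for Aim 2 are a series of chi-square tests and qualitative analysis.

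The design is a randomised one. Study Design says: "Distribution of participants to the two groups will be randomized". Four couples start therapy at once and four wait 8 weeks (± 10 days). On Group 2's assessments it says "The participants that are assigned to Group 2 will also complete the physiological data collection before starting the 8 week waiting period" and, after the wait, "All the physiological and behavioral data collection will be repeated once Group 2 starts therapy".

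Other text implies a comparison of groups. The sample size paragraph assumes 4 couples per group and two waves of data, and gives the chi-square test of effectiveness a power of .40 at an effect size of .60. Safety Monitoring calls the waiting couples the control group. Data Monitoring gives Group 2 doing better than Group 1 as an example of a reason to modify or stop.

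**The concern.** The Purpose section asks whether couple therapy is effective. A fall in reported violence after therapy starts does not answer that. Violence may change without therapy, couples are assessed repeatedly, and Safety Monitoring gives stress and anger management training to all participants. The waiting group is there to remove drift common to both groups, but it does so only if the analysis uses it.

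The open choices also matter. The contrast, the two waves, the coding of IPV for a chi-square table and the unit are not fixed in the analysis text, while Data Monitoring has the investigator review data after every assessment session. Those choices could then be made after results are seen.

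**Working it through.** **1. The plan's own figure.** Inputs from the sample size paragraph: effect size .60 (labelled f, read here as w) and power .40. Alpha is not stated; 0.05 is assumed. With 1 df, the noncentrality is λ = N × w².

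- N = 8: λ = 8 × 0.36 = 2.88, power 0.396. This reproduces .40.
- N = 16: λ = 16 × 0.36 = 5.76, power 0.670.

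So the figure fits eight independent units and not 16. With 4 couples per group in the same paragraph, this points towards group by outcome on 8 couples. It is not proof, since 8 partners of one sex would fit equally well.

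**2. Are the data for a randomised contrast collected?**

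- Group 1: a pre-test before therapy, and a post-test one week (± 5 days) after therapy ends.
- Group 2: a pre-wait session, then a repeat of all data collection around the start of therapy.
- Behavioral Measures puts IPV questionnaires at each visit, and Screening Measures says the CTS2 is used throughout the study.

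The four assessments therefore exist. Two details need attention. "All the physiological and behavioral data collection will be repeated once Group 2 starts therapy" could be read as after the first session, whereas Study Design elsewhere places the pre-test before therapy sessions begin. The two intervals are also close but not identical.

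**3. Precision with a continuous couple score, 4 v 4 couples, two-sided 0.05.** The half-width of the 95% CI, in SDs of change, is t(0.975, df) × √(1/n₁ + 1/n₂).

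- 4 v 4: 2.447 × √(1/4 + 1/4) = 1.73.
- One couple lost (3 v 4): 1.96. One lost per group (3 v 3): 2.27.
- Power at d = 0.8 (noncentral t, 6 df, noncentrality 0.8 × √2 = 1.13): 0.16.
- d needed for 40% power: 1.43. For 80% power: 2.38.

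For comparison, a before/after change on all 8 couples has half-width 2.365/√8 = 0.84 SD of change. It looks twice as precise but answers a different question.

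**4. Precision if IPV is dichotomised, exact test on 4 v 4.**

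- 4/4 v 0/4: p = 2/70 = 0.029.
- 3/4 v 0/4 and 4/4 v 1/4: p = 2 × 4/56 = 0.143 each.

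Only complete separation reaches 0.05. At assumed rates of 80% v 20% (w = 0.60, the plan's effect size), the exact power is 0.8⁴ × 0.8⁴ = 0.168, plus a negligible term for the opposite direction. The plan's .40 does not carry over to an exact test.

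**5. Recall period and zero counts.** Exclusion criterion 1 removes couples reporting a violent behaviour at least six times in a year, so an eligible act occurs at most 5 times a year. As an illustration only, take a recall period equal to the shortest permitted wait, 56 − 10 = 46 days. The expected count per act is then at most 5 × 46/365 = 0.63. If counts are Poisson, at least e^(−0.63) = 53% are zero even at baseline. Summing acts or including psychological items would reduce this.

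**The case against.** The plan calls itself an initial feasibility study collecting pilot data, so confirmatory detail is not to be expected. With power of 0.16 at d = 0.8, the randomised contrast cannot settle effectiveness. Much is already in place: IPV at each visit, a pre-test before therapy, and an instruction to obtain end-of-study assessments from couples who discontinue. Figure 1 and the body of Table 2 are not shown and may list the visits. The chi-square power also goes some way towards a group table on 8 couples.

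Most of this stands, and it limits the point rather than removing it. The same section still announces a test of effectiveness, and a visit schedule would not ordinarily define a contrast or the coding of an outcome.

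Several stronger readings are tempting but unsupported:

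- That the trial has no group comparison at all. One is implied in several places; it is undefined, not absent.
- That the t-test power statement shows confusion about Aim 2. The plan assigns t-tests to Aim 1.
- That partners will be pooled as 16 independent people. The plan says "This aim will examine the effect of couple therapy on each individual partner separately", and the chi-square power fits 8.
- That CTS2 recall at the outcome visits reaches back a year. That time frame appears only in an exclusion rule.
- That any fall seen would be drift. The documents give no figure for its size or direction, and regression to the mean may be small because baseline is a separate session after screening.

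**Conclusion.** The point holds as a matter that should be fixed. Both statements of Aim 2 are before/after questions, the design supplies a randomised waiting group, and the analysis text does not define the comparison that would use it. As worded, Aim 2 cannot attribute a change in violence to therapy.

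The randomised contrast is the better analysis on data already planned, but it will be imprecise: about ±1.73 SD of change with all 8 couples. These figures assume two-sided 0.05, roughly normal couple-level change scores and no loss. No size of bias is claimed for the before/after analysis. The contrast removes only drift common to both groups. Reporting bias from unblinded self- and partner-report remains. So does any effect of extra measurement during therapy, when "participants will complete a small number of assessments at each therapy session".

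**What to change.** In the Data analysis plan:

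- Make the effectiveness contrast for Aim 2 Group 1 v Group 2 as randomised, with the couple as the unit: change in IPV from baseline to post-test in Group 1 against change from the pre-wait baseline to the pre-therapy assessment in Group 2.
- Name the CTS2 scale used and how the two partners' reports are combined. Use the same recall period in both groups at the compared visits; the investigators should choose it.
- Reconcile the two statements on timing so that Group 2's second assessment precedes session 1.
- Report the difference with a 95% CI as a pilot estimate. If the chi-square is kept, replace it with an exact test of group by outcome on 8 couples; if not, revise its power sentence. The .40 should not be carried over to an exact test.
- Give partner-specific results separately for women and men, which is possible because "Only heterosexual couples will be included in the study".
- Label as descriptive the pooled before/after change, Group 2's post-therapy change and the 3-month follow-up.

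The cost is a rewritten Aim 2 paragraph, a matching sample size sentence, one timing sentence and one CTS2 instruction. No visits or couples are added. The price is the wide interval shown above, and a short recall period risks many zero counts.

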Mouth swipes will be used to measure saliva cortisol. Participants will be asked to place the oral swab into their mouth (under tongue), keep in place for 1 minute, and put the oral swab into the collection kit tube. eMotion HRV will be used to measure heart rate variability. eMotion HRV Sensor is an internally powered heart rate variability measurement device. During measurement, the sensor will be connected to the patient via two electrodes. The electrodes will be placed approximately along the electrical axis of the heart. The negative electrode (yellow) will be placed in the right infraclavicular fossa (just below the right clavicle). The positive electrode (red) will be placed on the left side of the chest, below the pectoral muscle in the left anterior auxiliary line. The research personnel will start the measurement by pushing the sensor power button down for one second. The green indicator light will light up and start blinking synchronously with the heart rate. At the end of the measurement, the research personnel will push the power button continuously for five seconds to end the measurement. The sensor will power down and the green indicator light will turn off.

Finally, each partner will complete questionnaires composed of the measures described below. It is expected that the lab session will last two hours. Participants will also complete measures on variables that may influence cortisol, such as conflict, unusual events, caffeine consumption, or exercise patterns (Kudielka, & Kirschbaum, 2003). After they finish completing all of the questionnaires, the therapist will instruct them in relaxation techniques and interventions to help deal with any negative emotions before they leave the assessment session.

The same procedure will be followed for each assessment phase (pre-test, post-test, and follow-up) and will take place during the hours of 4 pm to 8 pm because that is when the body's Circadian rhythm causes cortisol levels to normalize.

CTSC Dahms clinical unit will process and analyze the cortisol levels. The PI is in contact with [name], [name], and [name] for utilizing the Dahms Clinical Unit. For interpretation of the data, the PI is receiving consultation from [name] from Kent State University Department of Psychology. Please see the attached letter of commitment from [name].

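### Aim 2 asks for the effect of couple therapy but names no comparator; the randomised wait-list contrast, whose recordings are already scheduled, is implied but not defined

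*Combined protocol and SAP*

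**What the plan says.** **The aim.** The Purpose section states Aim 2 as "Examine the longitudinal effects of conjoint therapy on IPV" and on each partner's physiology, and adds: "This aim will examine the effect of couple therapy on each individual partner separately". That is causal wording.

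**The analysis.** The Data analysis plan gives the objective of Aim 2 as "whether violence decreases over time following therapy and whether this decrease is accompanied by respective change in physiological markers of emotion regulation". The methods are a series of chi-square tests and qualitative analysis. No table layout, time points or comparison group is given.

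**The design.** Under Study Design, eight couples form two groups of four, and "Distribution of participants to the two groups will be randomized". Group 1 starts therapy at once. Group 2 waits eight weeks, give or take 10 days, and is recorded before the wait and again as therapy begins. The Safety Monitoring text calls Group 2 the control group.

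**Hints of a group comparison.** The sample-size paragraph assumes "Assuming 8 couples (16 participants), with 4 couples in each group and two waves of data each" and names a chi-square test as the means of judging whether the intervention works. Data Monitoring gives, as an example of a reason to stop, Group 2 faring better than Group 1. None of these states an outcome, a pair of time points or a contrast.

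**Teaching outside therapy.** Under Physiological Measures, once recordings and questionnaires are done, "the therapist will instruct them in relaxation techniques and interventions to help deal with any negative emotions before they leave the assessment session". The section continues: "The same procedure will be followed for each assessment phase (pre-test, post-test, and follow-up"). Safety Monitoring has every participant taught stress and anger management, and Study Design describes such teaching again for Group 2. The text shown does not date this separate training. Under Recruitment, some information on the techniques is given at the initial interview, before any recording.

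**The concern.** A couple's change from pre-test to post-test contains more than therapy. Weeks pass, the conflict task and questionnaires are repeated, and relaxation is taught at the end of the pre-test session, hence before the post-test. Any of these could move reported violence, cortisol or vagal measures without therapy doing anything. If Aim 2 is reported only as change following therapy, a reader cannot separate these parts, although the aim promises the effect of therapy.

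What is at stake is modest but real. The protocol hopes the results will lead to larger effectiveness studies. A pilot figure carried into such a study should estimate therapy against no therapy, and the randomised design can supply that.

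**Working it through.** **1. The plan's own figures.** Alpha and sidedness are not stated; two-sided .05 is assumed throughout.

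- Chi-square, effect .60 (taken as w), stated power .40. Noncentrality = N × w². With N = 8 and 1 df: 8 × .36 = 2.88, power .396. This reproduces and fits a 2×2 table of eight couples. It does not prove that layout: N = 16 with 5 df gives .416, and N = 16 with 1 df gives .670.
- t-test, effect .80, stated power .40. Read as d, 4 v 4 gives .160 and 8 v 8 gives .320. Read as f (d = 1.6), 4 v 4 gives .476. None of these matches, so this figure does not reveal the intended comparison either.

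**2. What is recorded** (Study Design, Physiological Measures, Safety Monitoring).

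| | First recording | In between | Second recording |
|---|---|---|---|
| Group 1 | pre-test | eight weekly therapy sessions; relaxation teaching after the pre-test; stress-management training, undated | post-test, one week (±5 days) after therapy |
| Group 2 | before the wait | waiting; safety planning and stress and anger management teaching, undated; relaxation teaching, if the pre-wait session follows the standard procedure | as therapy begins |

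The physiological recordings for both halves of a randomised contrast are scheduled. Violence questionnaires at the pre-wait session are implied, since Group 2 has an extra baseline assessment and its behavioural data are later repeated, but the text shown does not list them.

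**3. What each analysis estimates.** Let T be the mean effect of the therapy package. Let S1 and S2 be the mean change from everything else in Groups 1 and 2 between the first and second recordings.

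- Before/after in Group 1: T + S1.
- Group 1 change minus Group 2 change: (T + S1) − S2, which equals T when S1 = S2.

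The contrast removes what the groups share. It does not remove a difference in teaching or in the length of the interval.

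**4. Precision,** for men and women separately, in SD of change, with no dropout and equal SD.

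- 4 v 4 contrast: t(6, .975) × √(1/4 + 1/4) = 2.447 × .707 = 1.73.
- Before/after, Group 1 alone: t(3, .975) / √4 = 3.182 / 2 = 1.59. The contrast is 1.73 / 1.59 = 1.09 times as wide.
- Before/after, both groups pooled across their therapy periods: t(7, .975) / √8 = 2.365 / 2.828 = .84. The contrast is about 2.1 times as wide, but the pooled figure still contains the non-therapy change.
- Power of the contrast (noncentral t): .16 at d = .80. Power .40 needs d = 1.43, and power .80 needs d = 2.38.
- A yes/no outcome by Fisher's exact test: 4/4 against 0/4 gives p = 2/70 = .029. 4/4 against 1/4 gives p = .14, so only a complete split falls below .05.

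**5. Illustration.** Suppose T = 0 and S1 = s SD of change. A one-sample t-test on Group 1 (n = 4, noncentrality 2s, 3 df) gives p < .05 with probability .05, .07 and .11 at s = .1, .3 and .5. Both the test and the range of s are assumptions: the plan names no t-test for Aim 2, and the documents give no value for s. The 4 v 4 test stays at .05 if S1 = S2.

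**The case against.** The strongest reply is that the comparison is already intended. Couples are randomised, Group 2 is called the control group, power is argued with four couples in each group, and the chi-square test is tied to whether the intervention works. The chi-square figure also reproduces for eight couples with one degree of freedom. This largely stands as a reading of intent. It does not supply the outcome, the time points or the contrast, so the point is about an undefined comparison.

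A reader might infer that the plan commits itself to an uncontrolled before/after test. The documents do not support that, because the Aim 2 table layout is left open.

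A reader might also infer that the relaxation teaching is known to distort the results. It follows a conflict discussion and is described as help with negative emotions before going home. Nothing gives it a lasting effect. It is one plausible contributor beside time and repeat testing, and the project flow chart and assessment schedule, which are not shown, may settle the timing of the other training.

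Finally, 4 v 4 is very small. That stands, and it is why the contrast is proposed as an estimate with an interval.

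**Conclusion.** The point holds as a minor one. Aim 2 asks a causal question, its analysis names no comparator, and the randomised contrast that would answer it can be added from data the study already plans to collect. The cost is an interval of about ±1.73 SD of change and power of .16 at d = .80, so the result describes and does not test efficacy.

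The conclusion assumes that Group 2's pre-wait session includes the violence measures. For the contrast to isolate therapy, it also needs non-therapy change to be similar in the two groups.

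Two stronger readings should not be drawn.

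- The recording intervals are not shown to match. The first recording is dated only as "Baseline Pre-test: Before starting the therapy sessions", or as before the wait, with no window.
- A false-positive rate for both groups' before/after changes pooled is not supported. Group 2 has been taught before its pre-therapy recording, so its training shift during therapy need not equal that of Group 1.

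**What to change.** 1. **Data analysis plan, Aim 2.** Add the randomised contrast: change from first to second recording, Group 1 (pre-test to post-test) against Group 2 (pre-wait to pre-therapy), for violence and for physiology, for each partner, as a difference with its 95% interval. Keep the planned chi-square and qualitative work. Keep the before/after change too, but state that it is not interpreted alone as the effect of therapy.
2. **Name what is compared.** This is the therapy package, including between-session calls, individual safety checks and anger-control content (Safety Information), against waiting with stress-management teaching.
3. **Study Design and Safety Monitoring.** Confirm that Group 2's pre-wait session includes the violence questionnaires, and that its second recording precedes the first therapy session. Log the dates of all training and recordings. Training needed for safety goes ahead regardless and is logged.

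The cost is a few sentences and a date log, with no extra visits or measures. The downside is the very wide interval, which should be stated beside the estimate.
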